12.9 Final Analysis

We will compare the difference in antibiotic use between groups by a one-sided test comparing the mean duration of antibiotic use. We will also compare the DOOR distribution between groups, and the DOOR probability of having a more desirable outcome in intervention group versus control. A DOOR probability of 50% will indicate no statistical difference between groups. We will additionally calculate the probabilities specific to each component (AE, infectious complications, etc), using methods described in prior studies⁵⁷. We will further perform descriptive analyses for secondary outcomes, and modeling to examine whether confounding factors (Age, qSOFA or Charlson comorbidity scores) impacted estimates of intervention effect and safety. Randomization quality will also be evaluated for potential differences between arms for baseline variables. Chi-Square tests will be used for categorical measures and t-tests or Wilcoxon tests for continuous measures.

We anticipate that the percentage of missing data will be negligible as the outcomes of interest are part of routine data collection in the ICU setting and the observation period of interest is while the patient is in the hospital. In the event some data is lost (eg. Medical chart is misplaced or lost, electronic medical data inadvertently deleted), we will not replace those lost to follow-up and the data from those participants will be included in the Intention-to-Treat analysis. We will also conduct a sensitivity analysis of those lost to follow-up to ensure there is no systematic bias.

12.10 Sub-Group Analyses:

Studies have shown significant gender differences in antibiotic use with women being 27% more likely to receive antibiotics in their lifetime than men⁶³. This has at least in part been attributed to health-seeking behavior, and gender disparities tend to diminish with older age and comorbidities⁶⁴. More recently, studies conducted in the US have shown significant disparities in rates of inappropriate antibiotic prescriptions related to race and ethnicity, with blacks and Hispanics more at risk of receiving inappropriate prescriptions than whites⁶⁵. We will specifically conduct subgroup analyses to determine if sex, gender, ethnicity impact not only antibiotic prescription quality and clinical outcomes, but also the treating team's adherence to BV-guided treatment recommendations. Our study sites service a large proportion of the First Nations, Inuit and Metis populations of Quebec, with medivac transfers for procedures and hospitalizations.

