7. RANDOMIZATION AND BLINDING PROCEDURES

7.1 Randomization

Eligible participants will be randomized in a 1:1 ratio to either the intervention or control groups. Randomization will be stratified by study center to account for site-specific participant characteristics and physician practices. This stratification ensures that any potential confounding factors associated with the different sites are balanced across the treatment groups.

To further ensure the randomization process is robust, block randomization will be utilized within each site. The blocks will have varying sizes, determined by an internet-based randomization tool, to prevent predictability and maintain the integrity of the allocation process. The specific block sizes will remain undisclosed to the research team and participants to ensure concealment and prevent potential bias.

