8.4 Baseline Visit (Day 0)

Study team (Pharmacist and PI/Co-I) perform a clinical assessment of the participant to establish a baseline assessment of the antibiotic prescription (indication and appropriateness of antibiotic) and enter the assessment into the eCRF.

- Collect the following data on participant:
 - o Antibiotics prescribed (start and end dates, name, dose)
 - o Microbiological results
 - o Colonization status for MDRO
 - o Signs and symptoms of infection
 - o Adverse events related to antibiotics if any
 - o Laboratory values for creatinine, liver, hematology
- Research Blood Collection; Collect up to 5 mL (1 teaspoon) of blood for research laboratory BV testing and analysis

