12.4 Sample Size and Justification

DOOR-RADAR requires fewer patients than conventional non-inferiority analysis but since a major objective of this study is to enable a detailed analysis of adverse events related to antibiotic use, we have calculated a sample size that would enable separate analysis of clinical outcomes and antibiotic use (Sample size calculations detailed in Appendix I).

Testing hypothesis 1 (H1): We desire at least 80% power to test our primary hypothesis that BV-supported antibiotic treatment decision can lead to reducing antibiotic exposure using a one-sided significance of 0.05. Demonstrating H1 would require a sample size of 352 participants per group for a mean difference in antibiotic days of 1.5 (SD 8 days). Based on studies evaluating AMS interventions in the ICU, we estimate a 1.5 days difference between the 2 groups to be significant^{14,18,36}. Further, it would be equivalent to a 20% decrease in total antibiotic days, a reasonable assumption considering antibiotics are “clearly not indicated” or “only somewhat (dubious) indicated” in about 30% of cases based on prior retrospective audits of prescription quality.

Testing hypothesis 2 (H2): BV-supported antibiotic treatment algorithm does not lead to worse clinical outcomes. Studies using combined endpoints of adverse outcomes have estimated between 10-25% rates of combined adverse outcomes (death, septic shock, mechanical ventilation, renal failure)^{38,42,43}. A meta-analysis of PCT-guided antibiotic treatment in patients with infection and sepsis in ICU reported all-cause mortality rates of 23% at 30-days³⁵. Studies evaluating adverse events specifically related to antibiotic use in hospitalized patients suggest rates of 12% within 30 days. We expect a combined adverse outcome rate of 18-20% and will set a non-inferiority margin at 4%. A sample size of 529 patients per group (1060 in total) will therefore provide 80% power to demonstrate H2 (a robust safety evaluation), and yet be exceptionally well powered for efficacy (with preserved power under a wide range of assumptions).

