57. Howard-Anderson, J. *et al.* Moving Beyond Mortality: Development and Application of a Desirability of Outcome Ranking (DOOR) Endpoint for Hospital-Acquired Bacterial Pneumonia and Ventilator-Associated Bacterial Pneumonia. *Clin. Infect. Dis.* ciad576 (2023) doi:10.1093/cid/ciad576.
58. Howard-Anderson, J. *et al.* Improving Traditional Registrational Trial End Points: Development and Application of a Desirability of Outcome Ranking End Point for Complicated Urinary Tract Infection Clinical Trials. *Clin. Infect. Dis.* **76**, e1157–e1165 (2023).
59. Doernberg, S. B. *et al.* Good Studies Evaluate the Disease While Great Studies Evaluate the Patient: Development and Application of a Desirability of Outcome Ranking Endpoint for Staphylococcus aureus Bloodstream Infection. *Clin. Infect. Dis.* **68**, 1691–1698 (2019).
60. Tamma, P. D., Avdic, E., Li, D. X., Dzintars, K. & Cosgrove, S. E. Association of Adverse Events With Antibiotic Use in Hospitalized Patients. *JAMA Intern. Med.* **177**, 1308–1315 (2017).
61. DeMets, D. L. & Lan, K. K. G. L an- DE METS Alpha-Spending Function. in *Wiley Encyclopedia of Clinical Trials* (eds. D’Agostino, R. B., Sullivan, L. & Massaro, J.) 1–10 (Wiley, 2008). doi:10.1002/9780471462422.eoct394.
62. Schröder, W. *et al.* Gender differences in antibiotic prescribing in the community: a systematic review and meta-analysis. *J. Antimicrob. Chemother.* **71**, 1800–1806 (2016).
63. Smith, D. R. M., Dolk, F. C. K., Smieszek, T., Robotham, J. V. & Pouwels, K. B. Understanding the gender gap in antibiotic prescribing: a cross-sectional analysis of English primary care. *BMJ Open* **8**, e020203 (2018).

64. Young, E. H. *et al.* National Disparities in Antibiotic Prescribing by Race, Ethnicity, Age Group, and Sex in United States Ambulatory Care Visits, 2009 to 2016. *Antibiotics* **12**, 51 (2022).

18. Appendix I: Sample Size Calculations

For all calculations below – Type I error = 0.05, Power = 0.8, One-sided test

Sample size required for Hypothesis 1 that BV-supported antibiotic treatment recommendation leads to reducing antibiotic exposure.

Expected difference in mean # of days on antibiotics	Standard deviation of Days of antibiotics in ICU	Sample size required per group
1.5 days	10 days	550
1.5 days	8 days	352
1.5 days	6 days	198
1.5 days	4 days	89

Sample size required for Hypothesis 2 that BV-guided antibiotic treatment recommendation does not lead to worse clinical outcomes.

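### Randomization is stratified by center, but the primary comparisons named carry no site term and the blinded Day 0 necessity rating enters no treatment-effect analysis; the cost is a small loss of precision

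*Protocol*

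**What the plan says.** Protocol 7.1: "Randomization will be stratified by study center to account for site-specific participant characteristics and physician practices". Blocks of varying size are used within each site.

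Protocol 12.9, on antibiotic use: "We will compare the difference in antibiotic use between groups by a one-sided test comparing the mean duration of antibiotic use". The same section compares the DOOR distribution and the DOOR probability between groups. The synopsis names the Wilcoxon-Mann-Whitney statistic with a two-sided 95% interval. None of these names a stratum or a covariate.

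Covariates appear once, in 12.9, as supplementary "modeling to examine whether confounding factors (Age, qSOFA or Charlson comorbidity scores) impacted estimates of intervention effect and safety". Site is not in that list.

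Protocol 8.4 has the study pharmacist and an investigator "perform a clinical assessment of the participant to establish a baseline assessment of the antibiotic prescription" on Day 0. The schedule in 8.2 puts randomization on Day 1, 7.2 keeps the assessors blinded, and 8.8 requires the form for all participants. The resulting four-level necessity rating forms the rows of the decision matrices in 8.9 and 8.10.

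**The concern.** The design treats site as a predictor of outcome, balances on it, and then names comparisons that ignore it. When allocation is balanced within a predictive stratum, the between-stratum variance no longer contributes to the error of the treatment difference. An unstratified test still counts that variance in its standard error, so the interval is too wide and the test too cautious.

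The necessity rating is a separate matter. It is not a stratification factor, so leaving it out keeps the test at its nominal level but gives up precision if the rating predicts antibiotic days. Protocol 12.4 gives reason to expect that it does: it supports the hoped-for effect by the roughly 30% of cases in which antibiotics are not, or only doubtfully, indicated.

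At stake is precision that costs nothing to obtain. It matters more for H2, the non-inferiority question with the smaller power reserve.

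**Working it through.** **1. The plan's own figures.** Appendix I states "Type I error = 0.05, Power = 0.8, One-sided test", so z = 1.645 and 0.842.

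- H1 (difference 1.5 days, SD 8): n = 2 × 8² × (1.645 + 0.842)² / 1.5² = 351.7, hence 352 per group, as stated in 12.4.
- H2 (18% v 20%, margin 4 points): n = (0.20 × 0.80 + 0.18 × 0.82) × (1.645 + 0.842)² / (0.04 + 0.02)² = 528.3, hence 529. This agrees with "A sample size of 529 patients per group (1060 in total) will therefore provide 80% power to demonstrate H2".

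Both are unadjusted formulas.

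**2. Baseline at the planned 600 per group (4.1).** SE = 8 × √(2/600) = 0.462 days. The 95% half-width is 1.96 × 0.462 = 0.905 days. Power for 1.5 days is Φ(1.5/0.462 − 1.645) = 94.6%.

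**3. Site.** The protocol gives no site difference, so D = 0 to 4 days is assumed. Recruitment shares are assumed to follow the ICU beds in 14.3: w = 24/56 = 0.43. Then R² = w(1−w)D²/64, interval width scales by √(1−R²), and the one-sided size of the test without site is 1 − Φ(1.645/√(1−R²)).

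| Assumed D (days) | R² | Interval narrower by | Size without site | Power with site |
|---|---|---|---|---|
| 0 | 0% | 0% | 0.050 | 94.6% |
| 1 | 0.4% | 0.2% | 0.050 | 94.6% |
| 2 | 1.5% | 0.8% | 0.049 | 94.8% |
| 3 | 3.4% | 1.7% | 0.047 | 95.2% |
| 4 | 6.1% | 3.1% | 0.045 | 95.6% |

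Some of this gain comes from the stratified allocation itself. At D = 4 the test without site already has power Φ((1.5/0.462 − 1.645)/0.969) = 95.1%, so naming site in the analysis adds about half a point.

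A simulation of 1,200 participants (assumed blocks of 4 and 6, D = 4) gave size 0.0435 without site and 0.0478 with it, and half-widths of 0.905 and 0.877 days.

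**4. Necessity rating.** Assume a 30/70 split (the 30% of 12.4) and a difference of D days in mean antibiotic use, so R² = 0.3 × 0.7 × D²/64.

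| Assumed D (days) | R² | Interval narrower by |
|---|---|---|
| 2 | 1.3% | 0.7% |
| 4 | 5.2% | 2.7% |
| 6 | 11.8% | 6.1% |

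**5. Both together, H1.** At a total R² of 5% the half-width is 0.882 days and power 95.4%; at 10%, 0.859 days and 96.2%. With a 2-day site difference and a 4-day rating difference, simulated half-widths were 0.905 (unadjusted), 0.898 (site) and 0.874 (both).

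**6. H2 at 600 per group.** SE = √(0.3076/600) = 0.0226. Power is Φ(0.06/0.0226 − 1.645) = 84.3%. Multiplying the variance by (1−R²) gives 84.9%, 85.9% and 87.5% at R² of 2%, 5% and 10%. If the true rates were equal at 20%, for which Appendix I asks 1,238 per group, power would be 53.5% unadjusted and 57.2% at R² of 10%.

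**The case against.** The strongest reply is that the protocol is silent rather than wrong. A one-sided test of means does not exclude a site term, and stratum terms are commonly left to a statistical analysis plan, which is not at hand. It is fair that nothing in the text forbids site. But 12.9 goes beyond silence: it fixes a covariate list, and that list leaves out the one factor that the design singles out. A statistical analysis plan that followed this text would inherit the omission.

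The second reply is that the error is small and in the safe direction. That stands, and it sets the weight of the point.

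Four stronger readings are tempting, and the document does not support them:

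- **Adjustment depends on baseline tests.** A reader might infer that modeling is optional and follows tests of baseline balance, leaving the model open to choice. In 12.9 the modeling is planned outright and is mentioned before the evaluation of randomization quality. The only looseness is the choice between qSOFA and Charlson.
- **The rating goes unused.** It drives the recommendations in both arms. It is absent only from the treatment-effect analyses.
- **The gain in power is large.** That needs a high R² or an effect below the design value of 1.5 days. The protocol supplies neither. Even a 4-day site difference gives an R² of only 6.1%, and a 6-day rating difference 11.8%.
- **A longer adjusted model costs nothing.** The data lists in 8.3, 8.4 and 8.11 do not name qSOFA or mental status. Only site and the rating are plainly at hand for everyone.

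**Conclusion.** The point holds as a modest mismatch between design and stated analysis. Site is a randomization stratum but is in no named comparison, and a valid pre-randomization covariate is left out of every treatment-effect analysis. The consequence is lost precision: about 0-3% of interval width from site and 1-6% from the rating. Omitting site also makes the tests slightly conservative, with a one-sided size of 0.045-0.050. There is no bias and no inflation of type I error, and H1 is amply powered either way. The gain for H2 is about 1 to 3 points of power at the planning rates.

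These sizes rest on assumed differences, an SD of 8 days, and recruitment in proportion to beds. The protocol gives no figure from which the explained variance could be computed. No stated sample size is wrong on this account.

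**What to change.** In Protocol 12.9:

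- Carry site in each primary comparison: a site term in the model for mean antibiotic days (H1), a site-stratified Wilcoxon test and DOOR probability, and a site-stratified or standardized risk difference with its interval (H2).
- Prespecify the Day 0 necessity rating, in its four levels, as a baseline covariate for H1 and H2.
- Keep the unadjusted results as sensitivity analyses.

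The synopsis line on statistical analysis should match. The cost is wording only: site and the rating are already recorded for every participant before allocation is disclosed, and the sample size stays as it is.

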3.2 Objectives

3.2.1 Primary Objective(s)

To evaluate the combined endpoint of efficacy and safety at 28 days (approximately 4 weeks). This will include:

- Efficacy: Assessed by the use of antibiotics.
- Safety: Assessed by clinical outcomes.

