8.7 End of Study Visit EOSV (Day 28 + 2 days)

If participant is discharged prior to Day 28, provide a BAST-ICU discharge packet (28-day antibiotic use diary and report any symptoms). Every effort should be made to complete the Day 28 visit by conducting a remote call.

- Collect the following data on participant:
 - Review adherence of antibiotic treatment recommendation.
 - Antibiotics prescribed (start and end dates, name, dose)
 - Microbiological results
 - Colonization status for MDRO
 - Signs and symptoms of infection
 - Adverse events related to antibiotics if any
 - Laboratory values for creatinine, liver, hematology
 - Vital status: date of death, date of discharge from ICU, date of discharge from hospital
 - Disposition upon discharge from ICU

- Final clinical outcomes and DOOR ranking

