9. CLINICAL AND LABORATORY EVALUATIONS

9.1 Clinical Evaluations

After informed consent has been obtained, a research member with appropriate training will record the listed information on the eCRF. The initial evaluation will document reasons for ICU admission, current presentation and symptoms, working diagnosis, the reason for antibiotic therapy, and results of laboratory and diagnostic investigations. Patients will be monitored for 28 days or until death, with an End of Study Visit (EOSV) conducted at the conclusion.

Data collected during follow-up visits will include antibiotic prescriptions, symptoms of infections, laboratory and radiological results from the treating team, and adverse events. Antibiotic data will be extracted from the APSS (Lumed) application, while clinical diagnosis and evolution data will be sourced from patient charts and direct observation. Adverse events will be reported as part of the primary safety outcome.

All data will be collected on an electronic case report form (CRF). Original study forms (source documents) will be kept on file at the study site. All data will be kept for at least 7 years after the study's close.

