12.5 Expected Study Recruitment Flow Chart

12.6 Estimations of Adverse Outcomes in ICU

- Combined severe (Grade IV) adverse events secondary to antibiotics (excluding renal): 5-10%
- Overall Acute kidney injury in ICU (all cause): 26-67%
- Drug induced liver injury: rare (16-19/100,000)
- All cause ICU Mortality: 3-28% (MUHC ICU mortality: 13%; median length of stay in (IQR): 3.2 days (1.5, 7.6))

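### Section 12.9 treats the hospital stay as the observation period, which contradicts the 28-day primary endpoint and the planned post-discharge follow-up; the final-visit windows also disagree

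*Protocol*

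**What the plan says.** **28 days, wherever the patient is.** Section 3.2.1 gives the primary objective as "To evaluate the combined endpoint of efficacy and safety at 28 days (approximately 4 weeks"), and the synopsis repeats this. Section 9.1 says "Patients will be monitored for 28 days or until death". Section 8.7 provides for patients who leave early: "If participant is discharged prior to Day 28, provide a BAST-ICU discharge packet (28-day antibiotic use diary and report any symptoms"), and "Every effort should be made to complete the Day 28 visit by conducting a remote call". The same visit records date of death, adverse events, antibiotics and the final DOOR ranking.

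**Hospital stay.** Section 12.9 expects negligible missing data on two grounds: that the outcomes are routinely collected in the ICU, and that "the observation period of interest is while the patient is in the hospital". Its examples of lost data are mislaid charts and deleted electronic records. It keeps those lost to follow-up in the intention-to-treat analysis and promises a sensitivity analysis of them.

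**Final-visit window.** Section 8.7 is headed "End of Study Visit EOSV (Day 28 + 2 days") and the schedule in Section 8.2 also gives + 2 days. The last row of the table in Section 9.2 is labelled Day 28 +/- 2.

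**Antibiotic use.** Section 3.2.1 places antibiotic use inside the 28-day endpoint, and Section 8.7 supplies a 28-day diary. Section 12.3 relates days of therapy to days in ICU, and the standard deviation column in Appendix I is for antibiotic days in ICU. On sources, Section 9.1 says "Antibiotic data will be extracted from the APSS (Lumed) application" and does not name the diary.

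**The concern.** The period over which the primary endpoint is counted should have one meaning. A team working from Sections 3.2.1, 8.7 and 9.1 would count a recurrence on Day 20 in a patient discharged on Day 10. A team working from Section 12.9 could leave it out.

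The events affected are those that stopping antibiotics might cause. Section 12.2 defines treatment failure within 72 hours of the end of antibiotics and infectious complications more than 72 hours after it; recurrence is also a later event. Any of these can fall after discharge.

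Hypothesis 2 is a non-inferiority claim with a fixed absolute margin of 4 percentage points. Events missed equally in both arms shrink the absolute difference while the margin stays put, so under-counting makes the claim easier to reach. Discharge also happens after randomization, so if its timing differed between arms, stopping the count there would give the arms unequal observation time.

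**Working it through.** **1. Passages side by side**

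| Item | Reading A | Reading B |
|---|---|---|
| Outcome period | 28 days (synopsis, 3.2.1, 8.7, 9.1) | Hospital stay (12.9) |
| Final visit | Day 28 to 30 (8.2, 8.7) | Day 26 to 30 (9.2) |
| Antibiotic use | 28 days, with diary (3.2.1, 8.7) | Days in ICU (12.3, Appendix I) |

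Each row is a contradiction on the page. A contact on Day 26 cannot establish status on Day 28; the loss is at most 2 days, 2/28 = 7.1% of the window, and only for patients contacted that early.

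**2. Does the ground for expecting little missing data hold?** Section 12.6 gives, in its ICU mortality line, a "median length of stay in (IQR): 3.2 days (1.5, 7.6"). Read as ICU stay, this means half of the sites' ICU patients have left the unit by about Day 3 and three quarters by about Day 8. Routine ICU collection therefore covers only a small part of 28 days for most patients. Hospital stay is not given, so the share discharged home before Day 28 cannot be computed. After discharge the information comes from the diary, the call and whatever care the patient receives. Several adverse-event definitions in Section 11.3 need laboratory or ECG values, and Section 9.3 says the study team orders no blood work beyond the BV sample.

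**3. The plan's own sample size.** Inputs from Section 12.4 and Appendix I: 18% (BV) against 20% (control), margin 4 points, one-sided alpha 0.05, power 80%.

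n = (z₀.₉₅ + z₀.₈₀)² × [p₁(1−p₁) + p₂(1−p₂)] / (margin − (p₁ − p₂))²

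= (1.645 + 0.842)² × (0.1476 + 0.1600) / (0.04 + 0.02)² ≈ 6.183 × 0.3076 / 0.0036 ≈ 528.3, rounded up to **529**, as stated. The sample size is not in error on this point.

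**4. Illustration of the consequence.** Assumption, not in the documents: a fraction f of adverse outcomes goes unseen equally in both arms, and those patients count as event-free. Take a true difference exactly at the margin, 24% against 20%.

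Observed rates: p₁ = 0.24(1−f), p₂ = 0.20(1−f). SE = √{[p₁(1−p₁) + p₂(1−p₂)]/n}. Chance of declaring non-inferiority = Φ{[0.04 − (p₁ − p₂)]/SE − 1.645}.

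For f = 20% and n = 529: p₁ = 0.192, p₂ = 0.160, difference 0.032; SE = √(0.2895/529) = 0.0234; (0.04 − 0.032)/0.0234 − 1.645 = −1.303; Φ = 9.6%.

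| f (assumed) | 529 per group | 600 per group |
|---|---|---|
| 0 | 5.0% | 5.0% |
| 10% | 6.9% | 7.1% |
| 20% | 9.6% | 10.0% |
| 30% | 13.5% | 14.3% |
| 40% | 19.1% | 20.5% |

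Under the planning case (18% against 20%, 529 per group) the power computed the same way moves from 80.1% to 81.4% at f = 20%, so a power calculation would not reveal the problem.

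**The case against.** The sentence in Section 12.9 explains why few data should be missing; it does not define the endpoint. The sections that do set follow-up agree on 28 days, and Section 8.7 gives real means of observing discharged patients: a diary with symptom reporting, a call, date of death, laboratory and microbiology results. Section 8.6 adds visits on Days 3, 7 and 14 without limiting them to inpatients. On a fair reading 28 days is the intended period, and Section 12.9 also promises a sensitivity analysis of those lost. All of this stands, and it makes the point a contradiction to be reconciled rather than a missing follow-up scheme.

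A reader might go further and infer that a survivor who cannot be reached is scored Rank 1. Section 12.1 gives every participant a DOOR, and Rank 1 requires none of the listed events, so the inference is understandable. No section states it, however. Rank 1 also requires survival and clinical benefit, and a blinded three-member panel reviews clinical outcomes.

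A reader might also infer that the intervention arm would go home earlier and so look safer. ICU length of stay is a secondary outcome, but nothing in the protocol says the strategy shortens hospital stay. That would in any case be a differential bias, distinct from the equal under-counting illustrated above.

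The objection does not remove the contradiction itself. The in-hospital statement is one of only two grounds for the missing-data expectation, and the other, routine ICU collection, does not reach Day 28 for most patients.

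**Conclusion.** The point holds as an internal contradiction about the period over which the primary endpoint is counted. Section 12.9 conflicts with the synopsis and Sections 3.2.1, 8.7 and 9.1. Section 9.2 conflicts with Sections 8.2 and 8.7; this is minor. The antibiotic measure has a parallel conflict between 28 days and days in ICU.

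The harm is conditional. It arises if the in-hospital reading is applied, or if post-discharge contact fails and unobserved time is treated as event-free. The direction is then towards no difference, provided events are missed about equally in both arms. The documents give no size: the 6.9% to 19.1% range for false non-inferiority (529 per group) rests on assumed missed fractions of 10% to 40%, which should not be read as an estimate for this trial. The documents do not support a claim that patients will be scored event-free by rule, or that a particular share will be lost after discharge. Because the wording bears on the primary comparison and is cheap to correct, it should be settled before outcomes are adjudicated or interim data are reviewed.

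**What to change.** 1. **Section 12.9:** delete the in-hospital statement and the expectation of negligible missing data that rests on it. State that the DOOR clinical outcomes are counted from randomization through Day 28 wherever the patient is, using the chart, the discharge diary and the call.
2. **Section 12.9:** state that survivors without a Day 28 contact are not assumed event-free and are covered by the sensitivity analysis already promised. The method can be left to the SAP.
3. **Section 9.2:** change the last row to Day 28 + 2, to match Sections 8.2 and 8.7.
4. **Sections 3.2.1, 8.7, 9.1, 12.3 and Appendix I:** state explicitly whether antibiotic use is measured over 28 days or over days in ICU, and name the data source for any time after discharge. This should be a deliberate choice: extending the count to Day 28 everywhere would conflict with the ICU-based measure in Section 12.3. The 1.5-day difference and 8-day standard deviation behind hypothesis 1 would then have to be confirmed for the new window.

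**Cost:** items 1 to 3 are wording, since the diary, the call and the sensitivity analysis already exist. The expectation of negligible missing data is given up, and the fraction of survivors without Day 28 contact has to be reported. Item 4 may need the hypothesis 1 inputs to be rechecked.
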